## 11.0 DRUG INFORMATION

### 11.1 Predniso(lo)ne

(Deltasone®, PredniSONE Intensol®, Rayos®, Meticorten®, Liquid Pred®, PEDIAPRED®, MILLIPRED®, OraPred ODT®)

#### 11.1.1 Source and Pharmacology

Prednisone and prednisolone are synthetic compounds closely related to hydrocortisone. Glucocorticoids produce widespread and diverse physiologic effects on carbohydrate, protein, and lipid metabolism, electrolyte and water balance, functions of the cardiovascular system, kidney, skeletal muscle, and the nervous systems. Glucocorticoids reduce the concentration of thymus-dependent lymphocytes (T-lymphocytes), monocytes, and eosinophils. Glucocorticoids selectively bind to the cortisol receptors on human lymphoid cells that are found in larger numbers on leukemic lymphoblasts. They also decrease binding of immunoglobulin to cell surface receptors and inhibit the synthesis and/or release of interleukins, thereby decreasing T-lymphocyte blastogenesis and reducing expansion of the primary immune response. The specific cellular mechanisms that act to halt DNA synthesis are thought to be related to inhibition of glucose transport or phosphorylation, retardation of mitosis, and inhibition of protein synthesis. Peak blood levels occur within 2 hours of oral intake. Prednisone is approximately 75% protein bound with a plasma  $t_{1/2}$  of 3.2 to 4 hours. (Biologic half-life is 12-36 hours.)

#### Predniso(lo)ne Toxicities:

	Common Happens to 21-100 children out of every 100	Occasional Happens to 5-20 children out of every 100	Rare Happens to < 5 children out of every 100
Immediate: Within 1-2 days of receiving drug	Insomnia, hyperphagia	Gastritis	
Prompt: Within 2-3 weeks, prior to the next course	Immunosuppression, personality changes (mood swings, euphoria, anxiety, depression), pituitary-adrenal axis suppression, acne (L)	Hyperglycemia, facial erythema, poor wound healing, infections (bacterial, fungal, parasitic, viral), edema	Pancreatitis (L), electrolyte imbalance (Na retention, hypokalemia, hypocalcemia) (L), increased intraocular pressure (L), hypertension, psychosis, vertigo, headache
Delayed: Any time later during therapy	Cushing's syndrome (moon facies, truncal obesity)	Striae and thinning of the skin, easy bruising, muscle weakness, osteopenia	Spontaneous fractures (L), growth suppression, peptic ulcer and GI bleeding, pseudotumor cerebri (increased intracranial pressure with papilledema, headache), aseptic necrosis of the femoral and humeral heads (L), urolithiasis  (L)
Late: Any time after completion of treatment		Cataracts (that may be reversible on discontinuation of prednisone in children)	
Unknown Frequency and Timing:	Fetal and teratogenic toxicities: Corticosteroids cross the placenta (prednisone has the poorest transport). In animal studies, large doses of cortisol administered early in pregnancy produced cleft palate, stillborn fetuses, and decreased fetal size. Chronic maternal ingestion during the first trimester has shown a 1% incidence of cleft palate in humans. Prednisone is excreted into breast		

	milk in humans; however, several studies suggest that amounts excreted in breast milk are negligible with prednisone doses $\leq$ 20 mg/day.
--	--

(L) Toxicity may also occur later.

#### 11.1.2 Formulation and Stability

Prednisone is available in 1 mg, 2.5 mg, 5 mg, 10 mg, 20 mg, and 50 mg tablets and as a solution in 1 mg/mL or 5 mg/mL concentrations. Inactive ingredients vary depending on manufacturer but tablet formulations may include calcium or magnesium stearate, corn starch, lactose, erythrosine sodium, mineral oil, sorbic acid, sucrose, talc and various dyes. The solution may include 5-30% alcohol, fructose, sucrose, saccharin, and sorbitol.

Prednisolone is available as 5 mg scored tablets (base) and 10 mg, 15 mg, and 30 mg orally disintegrating tablets (ODT; sodium phosphate [strength expressed as base]). Liquid formulations of prednisolone are available as 15 mg/5 mL oral solution (base); 5 mg/5 mL, 10 mg/5 mL, 15 mg/5 mL, 20 mg/5 mL oral solution (sodium phosphate [strength expressed as base]; and 15 mg/5 mL oral syrup (base). Inactive ingredients vary depending on manufacturer. Tablet formulations may contain dyes and liquid formulations may contain edetate disodium, methylparaben, saccharin sodium.

#### 11.1.3 Guidelines for Administration

See Treatment and Dose Modifications sections of the protocol.  
PredniSONE and prednisoLONE are equipotent corticosteroids.

#### 11.1.4 Supplier

Commercially available from various sources. See package insert for further information

## 12.0 CORRELATIVES/SPECIAL STUDIES

The goal of the planned laboratory correlative studies is to improve our understanding of the biological processes that drive GVHD and its clinical outcomes.

### 12.1 Sample Collection Guidelines

The correlative sample collection schedule is detailed in section 8 above. Serum will be collected in no additive, silicone coated glass or plastic tubes containing no anticoagulant (red or gold top tube). Non-real time samples (i.e., those that do not require overnight MAP analysis – screening, week 1, and week 2) will be processed at the participating center and batch shipped to GVHD Laboratory semi-annually for storage (in January and July). Further details are provided in Appendix A.

### 12.2 Assay Methodology

Assays will be performed according to the published MAGIC protocols.

### 12.3 Specimen Banking

Patient samples collected for this study will be stored indefinitely or until they are used up. If future use is denied or withdrawn by the patient, best efforts will be made to stop any additional studies and to destroy the specimens. In addition to the biomarker studies planned as part of this study, additional studies studying the underlying disease may be performed on the banked research samples as part of collaborations with other institutions and entities.

The specimens and their derivatives may have significant therapeutic or commercial value. The Informed Consent form contains this information and informs the subject that there is the potential for financial gain by the Icahn School of Medicine at Mount Sinai, the investigator or a collaborating researcher or entity.

The following information obtained from the subject's medical record may be provided to research collaborators when specimens are made available:

- Diagnosis
- Collection time in relation to study treatment
- Clinical outcome – if available
- Demographic data

### **13.0 DATA COLLECTION PLAN**

#### **13.1 Data Coordinating Center (DCC)**

Patients will be registered at the time of screening through an electronic data collection system (Electronic Research Application Portal, eRAP) maintained by the Icahn School of Medicine at Mount Sinai and used by the MAGIC DCC for clinical trials management. At the time of registration each subject, regardless of screening results, is assigned a unique six alphanumeric character identifier. Identifiers are used instead of subject names ensuring patient confidentiality with regard to all collected data and samples. Files that permit biospecimens, data, and records can be linked back to living individuals are available only at the enrolling site; the MAGIC DCC and laboratory personnel have no access to these files. All study correspondence and redacted source documents are electronically imaged and stored on a routinely backed-up, encrypted, password secured, computer server that sits behind a VPN-secured firewall that requires two-factor authentication to prevent intrusion. Research data files are stored within a clinical trial database created for this specific clinical trial, maintained by a dedicated information technology support team and protected by the same robust computer security protocols described above. Paper records are maintained in a locked file by the DCC regulatory team until they can be securely destroyed. All HIPAA protected information is maintained behind password-protected files at all times again using the same robust computer security protocols described above. Only HIPAA-certified personnel have access to individually identifiable information about human subjects. The private information and/or samples collected as part of this research will never be used or shared for future research unrelated to the study of GVHD or BMT, even if the identifiable information is removed.

#### **13.2 Case Report Forms (CRF)**

All data required to determine the safety, efficacy, and calculate each endpoint in section 9.1 will be submitted using the electronic case report forms located within the clinical trial subsection of the eRAP database for this trial.

#### **13.3 Patient Reported Outcomes (PRO)**

Patient reported outcome data will be obtained according to the schedule provided in the time and events table. Patients age 8 and older (and parental proxy surveys for patients age 5 to 17) will be administered six PROMIS surveys (see Appendix B) at each time point, thereby building the first multicenter quality of life dataset for pediatric patients with GVHD. Each test consists of 4 to 10 questions and the completion of all surveys will take less than 20 minutes. Surveys will be preferentially administered on paper and in-person but study staff will follow-up with patients

and parents to complete any missed surveys or missed questions by mail, email, telehealth, or telephone and surveys can be finalized by email, verbally, or by US mail.

Study staff at all sites will receive virtual training to ensure consistent procedures for collection of PROs. Staff will be trained regarding: 1) approaching participants; 2) administering PROs in-person, electronically, or via telehealth; 3) tracking study participants; and 4) minimizing missing data through timely review and persistent follow-up. PRO scores will be integrated into the database using a specifically designed module that includes the response to each survey question, as well as both the raw and standardized scores for each survey.

## **14.0 STATISTICAL CONSIDERATIONS**

### **14.1 Study Design/Study Endpoints**

This is a phase II, single arm, open-label, multicenter clinical trial to determine the effectiveness of a structured steroid taper, guided by serial biomarker and clinical response in pediatric patients with newly diagnosed, low-risk acute GVHD defined by standard risk clinical criteria (Minnesota) and low risk biomarkers (Ann Arbor 1). The primary study measure is the proportion of low-risk GVHD patients who achieve clinical response (CR, VGPR, or PR) on day 28 after being exposed to low cumulative dose of prednisone ( $\leq 13.5$  mg/kg) or other steroid equivalent during the first 4 weeks of therapy. A single arm phase II design was selected due to the relatively small numbers of allogeneic transplants performed in children.

To further investigate the treatment regimen, we will determine the proportion of patients who achieve a treatment response (CR, VGPR, or PR) by day 28, duration of response, the incidence of steroid refractory GVHD by day 100, and the cumulative steroid dose at days 28 and 90. Secondary endpoints will also include the cumulative incidence of serious infections, patient reported outcomes at days 28, 90, and 180, overall survival at 6 and 12 months, cumulative incidence of NRM at 6 and 12 months, relapse rate, and cumulative incidence of chronic GVHD requiring systemic steroid treatment by one year.

### **14.2 Sample Size and Accrual**

In this phase II clinical trial, our aim is to determine the effectiveness of a structured steroid taper, guided by serial biomarker and clinical response in pediatric patients with newly diagnosed, low-risk acute GVHD defined by standard risk clinical criteria (Minnesota) and low risk biomarkers (Ann Arbor 1). Under current practice, the mean cumulative steroid dose during the first four weeks of treatment is 27.1 mg/kg. A substantial reduction in steroid exposure by 50% or more would likely result in clinical benefit from less treatment-related toxicity. The expected proportion of low-risk acute GVHD patients whose cumulative prednisone (or other steroid equivalent) exposure during the first four weeks of treatment is  $\leq 13.5$  mg/kg (i.e., <50% of current practice) is 14%. MAGIC preliminary data indicates that 65% of patients with low risk GVHD ultimately have the ultra-low risk form of GVHD that should be amenable to substantial reductions in steroid exposure. A three-fold increase in the proportion of patients (from 14% to 42%) whose cumulative steroid exposure is  $\leq 13.5$  mg/kg would be clinically significant. A sample size of 50 low risk patients provides 90% power with an alpha of 0.001 to detect a difference of 0.28 (0.14 to 0.42) using a two-sided exact test in the proportion of low risk patients treated successfully with low steroid exposure.

The combination of the primary efficacy endpoint (overall response rate) and the secondary endpoints (response rate, duration of response, steroid-refractory GVHD, NRM, and serious infections) will be used to determine if this approach should be compared to the current standard

of unstructured steroid tapers in a phase III trial for patients with low risk GVHD. We will continuously monitor these outcomes and if at any point during this trial sufficient evidence emerges that the structured steroid taper is not likely to result in improvement in any of these parameters, the protocol committee will terminate the trial for futility.

Sample size calculations were performed using PASS 2020 Power Analysis and Sample Size Software (2020) NCSS, LLC. Kaysville, Utah, USA, [ncss.com/software/pass](https://www.ncss.com/software/pass).

The centers participating in this clinical trial collectively perform >300 allogeneic HCT per year. Based on data from the MAGIC database, we expect 105 patients will develop GVHD per year, including 90 with Minnesota standard risk GVHD. Although it is likely we will accrue faster, a conservative estimate is that we will consent and screen 50% of these cases (n=45), 65% of whom will have Ann Arbor 1 GVHD, which should result in 30 patients enrolled per year (approximately 2.5 per month). We also conservatively estimate that up to 5 patients will need to be replaced. We do not expect all centers to open to enrollment simultaneously and therefore we realistically expect to meet our accrual goals within three years.

### **14.3 Data Analysis Plans**

The primary endpoint is the proportion of patients who (1) achieve CR, VGPR, or PR by day 28 of treatment without additional immunosuppressive therapy and (2) whose cumulative prednisone exposure is  $\leq 13.5$  mg/kg. The proportion of patients who are successfully treated with  $\leq 13.5$  mg/kg cumulative prednisone dose will be compared to the historical control rate of 14% using a Chi-squared test.

All study patients will be analyzed and when appropriate, subset analyses by ultra-low risk and other patients will be performed. We expect 33 ultra-low risk patients and 17 other patients out of our sample size of 50 study patients, which will be sufficient for subset analyses.

Secondary outcomes such as the overall response rate, duration of response, cumulative incidence of steroid-refractory GVHD, incidence of serious infections (viral, bacterial, fungal, and parasite), cumulative steroid exposure at day 28 and day 90, overall survival at 6 and 12 months, cumulative incidence of NRM at 6 and 12 months, relapse rate at 6 and 12 months, and cumulative incidence of chronic GVHD requiring systemic steroid treatment by one year will be estimated and compared to historical controls.

Continuous variables will be summarized using standard summary statistics such as number of observations (n), mean, standard deviation (SD), minimum and maximum values, median, and 1st and 3rd quartiles. Categorical variables will be summarized in frequency tables as counts and percentages.

Cumulative incidence of non-relapse mortality will be estimated by Gray's method and relapse will be considered as a competing risk. Disease free and overall survival, defined as the time from the transplantation to death or to last follow-up if alive, will be estimated by the method of Kaplan-Meier and the probability curves and 95% confidence intervals will be provided based on the method of Brookmeyer and Crowley.

The exploratory endpoints of linear growth velocity and patient reported outcomes as per Appendix B will be described for patients whose cumulative steroid exposure is  $\leq 13.5$  mg/kg and  $> 13.5$  mg/kg. Linear growth velocity will be expressed as a standard deviation score of the sex- and age-specific mean.

Data from a randomized adult acute GVHD treatment trial suggests that QOL (both physical and mental functioning) diverges around day 90 among patients with different steroid exposures. We expect our measures to show greater and faster improvement in QOL in patients with less steroid exposure, but for completeness, we will track PROs until 180 days from GVHD onset. The day 180 time point may be confounded by steroid treatment for chronic GVHD in some patients, and subsets may thus need to be analyzed. Formal comparisons between groups are not planned but we will explore the possibility of creating groups according to cumulative steroid dose. If groups can be created, we will compare groups using the difference of half of a standard deviation (5 points) in PRO scores which has been validated as clinically meaningful. PROMIS instruments will be scored in accordance with the manuals ([https://www.healthmeasures.net/index.php?option=com\\_content&view=article&id=180&Itemid=994](https://www.healthmeasures.net/index.php?option=com_content&view=article&id=180&Itemid=994)) and the scores will be analyzed using generalized linear models. General hierarchical random effects linear mixed model will be employed with repeated measures nested within site to assess the change between groups in outcomes of interest across multiple time points. The model will also include a random intercept. Determination of model fit will be aided by diagnostics for model residuals. We expect that there will be some minor and major missing data. Minor missing data include missing values on individual survey items. Although we will endeavor to check all questionnaires upon their return and call the participants to try to complete missing items, some data may still be missing. These individual items will be imputed. The imputed values will then be used to obtain point estimates for the missing data. Since the proposed study is longitudinal, major missing data from participant attrition is more likely and, potentially, more problematic. Two different attrition strategies will be employed. In the first, a binary variable for dropout (Yes or No) will be created and we will develop a hierarchic logistic regression model for clustered data (hospital is the clustering variable) using generalized linear mixed models with a logit link function. Any demographic or medical variables identified during initial data screening predicting dropout will be entered first. In the next step, any PRO measures will be assessed as predictor of dropout. These analyses will address the generalizability of study results. Patient and parental proxy scores will be compared for the subsets where both scores are available (ages 8-17y). The QOL analyses will be conducted in collaboration with [name], co-investigator and an expert in the interpretation of pediatric PRO data at Emory University.

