	
premedication for transfusions/IV medications, or intermittent use for symptom control such as nausea/vomiting
 
 
3. Relapsed, progressing, or persistent malignancy or other condition (e.g., known declining donor chimerism) requiring withdrawal of systemic immune suppression or donor leukocyte infusion (DLI)
 
4. Patients with uncontrolled infection (i.e., progressive symptoms related to infection despite treatment, persistently positive microbiological cultures despite treatment, viral reactivations unresponsive to treatment, or any other evidence of severe infection)
 
5. Patient requiring mechanical ventilation or cardiac pressor support
 
6. A clinical presentation resembling de novo chronic GVHD or overlap syndrome developing before or present at the time of enrollment
 
7. Patients who are pregnant
 
 
*Patients on <math>\leq 0.5</math> mg/kg/day prednisone for <math>\leq 2</math> days for new onset GVHD can be eligible as delineated in section 6.0

Study Product(s), Dose, Route, Regimen	Prednisone (or equivalent) at a starting dose of 0.5 mg/kg/day orally or IV and dose adjusted according to clinical and biomarker responses
Duration of Administration	28 days
Statistical Methodology	
The primary study measure is the proportion of low-risk GVHD patients who achieve clinical response (CR, VGPR, or PR) on day 28 after being exposed to low cumulative dose of prednisone (<math>\leq 13.5</math> mg/kg) or other steroid equivalent during the first 4 weeks of therapy. The expected proportion of patients with low risk (Minnesota standard risk/Ann Arbor 1) GVHD whose steroid exposure is <math>\leq 13.5</math> mg/kg is 14%. Patients with low risk GVHD who have favorable clinical and biomarker responses during the first two weeks of treatment have excellent outcomes, represent 65% of low risk GVHD, and will undergo structured steroid tapers designed to reduce cumulative steroid exposure by 50% or greater. A three-fold increase in the proportion of patients (from 14% to 42%) whose cumulative steroid exposure is <math>\leq 13.5</math> mg/kg would be clinically significant. A sample size of 50 patients provides 90% power with an alpha of 0.001 to detect a difference of 0.28 (0.14 to 0.42) in the proportion treated successfully with reduced steroid exposure.

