### 3.2 Current Standard of Care for Pediatric GVHD

The Mount Sinai Acute GVHD International Consortium (MAGIC) is a collaborative effort among 21 academic adult and pediatric hematopoietic cell transplant centers in North America, Europe and Asia to study GVHD. In addition to interventional trials, MAGIC has been conducting a natural history trial since 2014 that has prospectively collected clinical data and research samples on 700 children who received a first allogeneic transplant including 250 who developed GVHD that required treatment. Consensus guidelines for GVHD treatment recommend high starting prednisone doses (1-2 mg/kg/day) and slow tapers every 5-7 days in responding patients resulting in a cumulative prednisone dose of 20-40 mg/kg in the first four weeks of treatment. MAGIC data confirms this calculation in pediatric patients whose mean cumulative prednisone exposure is 27.1 mg/kg ( $\pm 0.5$  mg/kg) in the first four weeks. The clinical response after 4 weeks of steroid treatment often serves as the primary endpoint in acute GVHD clinical trials and is a widely accepted surrogate for NRM and long-term survival. However, an early clinical response after one week of systemic treatment does not determine treatment success or result in less steroid exposure. MAGIC data showed that the cumulative steroid dose was the same in patients who responded rapidly within 7 days ( $26.9 \pm 2.1$  mg/kg) and those who did not ( $28.0 \pm 0.8$  mg/kg).

Our natural history study also shows that physicians only occasionally limit steroid exposure. For example, only 14% of children with low risk GVHD (described below) are treated with <50% of the mean prednisone steroid dose (i.e.,  $\leq 13.5$  mg/kg), even though their outcomes are as good as those observed in patients treated with greater steroid exposure. These data indicate that GVHD in children is often over-treated.

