### **4.4 Primary Endpoint**

Proportion of patients with low-risk GVHD (Minnesota standard risk/Ann Arbor 1) who are in CR, VGPR or PR on day 28 of treatment and whose cumulative prednisone (or other steroid equivalent) exposure during the first four weeks of treatment is  $\leq 13.5$  mg/kg (i.e.,  $<50\%$  of current practice).

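### Section 14.3 analyses the primary endpoint with a chi-squared test although 14.2 powers an exact test, and the 14% and 42% are worded as dose-exposure rates while the endpoint also requires response

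*Combined protocol and SAP*

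**What the plan says.** **Test.** Section 14.2 sizes the trial at 50 patients, for 90% power at alpha 0.001 against a rise from 0.14 to 0.42, and says that this was calculated "using a two-sided exact test in the proportion of low risk patients treated successfully with low steroid exposure". Section 14.3 says that the proportion treated successfully "will be compared to the historical control rate of 14% using a Chi-squared test", and gives no alpha, sidedness or continuity correction.

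**Endpoint.** Section 4.4 counts patients "who are in CR, VGPR or PR on day 28 of treatment" whose cumulative exposure over four weeks is also at most 13.5 mg/kg. Sections 14.1 and 14.3 define the same two-part endpoint, with the response part in 14.3 worded as "achieve CR, VGPR, or PR by day 28 of treatment without additional immunosuppressive therapy".

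**Source of 14%.** Section 3.2 reports from the natural history data that "only 14% of children with low risk GVHD (described below) are treated with <50% of the mean prednisone steroid dose". The synopsis attaches 14% to "The expected proportion of patients with low risk (Minnesota standard risk/Ann Arbor 1) GVHD whose steroid exposure is" at or below 13.5 mg/kg, and 14.2 does the same. None of these places adds a response condition.

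**Source of 42%.** Section 14.2 describes "A three-fold increase in the proportion of patients (from 14% to 42%) whose cumulative steroid exposure is" at or below 13.5 mg/kg as clinically significant. The primary objective (4.1.1) presents the same pair, 14% and 42%, as rates of successful treatment.

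**The concern.** Two separate mismatches bear on the primary analysis.

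First, the named test is not the one behind the stated alpha and power. With 50 patients and 7 expected successes under the null, a test at the 0.001 level works far out in the tail, where the normal approximation and the exact distribution need not give the same cut-off. If they differ, the plan holds two rejection rules, and the choice between them could be made after the data are seen.

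Second, a child who met the dose limit but did not respond would count towards an exposure-only rate and not towards the endpoint. If both 14% and 42% are exposure-only, the design describes a different quantity from the one to be tested, and the 90% power does not refer to the primary endpoint.

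**Working it through.** **Inputs.** n = 50, null 0.14, alternative 0.42, two-sided alpha 0.001 (14.2). Response rates in historical patients: 79% in low-risk GVHD (3.4), 96% in the ultra-low-risk group (3.5), 75% in the Ann Arbor 1 subset with stage 2 skin or isolated upper GI disease (3.8). X is the number of successes.

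**1. The plan's own power.** Find the smallest r with P(X ≥ r | 0.14) ≤ 0.0005.
- P(X ≥ 16 | 0.14) = 0.00093, too large.
- P(X ≥ 17 | 0.14) = 0.00029, so r = 17.
- P(X ≥ 17 | 0.42) = 0.9025, which reproduces the stated 90%.

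Ordering outcomes by their likelihood, instead of splitting alpha equally, also gives 17 as the upper cut-off. It adds 0/50 to the rejection region, for a total size of 0.00029 + 0.00053 = 0.00082.

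**2. The chi-squared test.** Assume a one-sample test against the fixed 14% at alpha 0.001. Expected successes are 50 × 0.14 = 7, and the variance is 7 × 0.86 = 6.02.
- At 16/50: (16 − 7)² / 6.02 = 13.46, p = 0.00024. With continuity correction: 8.5² / 6.02 = 12.00, p = 0.00053. Both reject.
- At 15/50: p = 0.0011, or 0.0022 corrected. Neither rejects.
- At 0/50: 49 / 6.02 = 8.14, p = 0.0043. There is no lower rejection region.

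| Test | Rejects at | True size, upper tail | Power at 42% |
|---|---|---|---|
| Exact, two-sided (14.2) | ≥17/50 | 0.00029 | 0.903 |
| Chi-squared (14.3) | ≥16/50 | 0.00093 | 0.944 |

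The exact two-sided p at 16/50 is 2 × 0.00093 = 0.0019 by doubling, or 0.00093 + 0.00053 = 0.0015 by likelihood ordering. Neither is significant at 0.001. In the upper tail the tests disagree only at 16/50, which has probability 0.0006 under 14% and 0.042 under 42%.

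**3. Benchmark and target on the composite scale.** Composite rate = exposure-only rate × proportion of low-dose children who respond. The documents give no response rate for the low-dose historical children; 3.2 says only that their outcomes were as good as the others'. The rates below are therefore assumptions.

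| Assumed response | Composite of 14% | Exact cut-off for that null | Composite of 42% | Power of ≥17/50 |
|---|---|---|---|---|
| 75% | 10.5% | ≥14/50 | 31.5% | 0.40 |
| 79% | 11.1% | ≥15/50 | 33.2% | 0.50 |
| 96% | 13.4% | ≥17/50 | 40.3% | 0.85 |
| 100% | 14.0% | ≥17/50 | 42.0% | 0.90 |

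A composite rate cannot exceed the exposure-only rate, so 14% is an upper bound for the null. At a true composite null of 11.1%, the ≥17/50 rule has upper-tail size 0.000015.

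**The case against.** The strongest reply is that the consequences are small. The null is 14% in the objective, the sample size and the analysis, so a reader who infers that the analysis uses a different null rate from the design would be wrong. The mismatch is between the 14% and the endpoint, and it is already present in 14.2. A reader might also infer that the chi-squared test inflates the type I error. It does not exceed the stated level: its total size is 0.00093. It does place more than 0.0005 in the upper tail, but no section allocates alpha by tail. An exposure-only 14% makes the test conservative. All of this stands.

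On power, the sample-size sentence itself refers to patients treated successfully, so 42% may have been meant as the composite rate. Also, 65% of low-risk patients are expected to be ultra-low risk, the structured tapers in Table 1 all list totals below 13.5 mg/kg, and 96% of that group responded historically. If that response held under the shorter tapers, the composite rate could be near 0.65 × 0.96 = 62%, and power would be high on any reading. That is a fair argument about what the trial may observe. It does not settle what the 90% at 42% refers to, and it assumes the result that the trial is meant to test.

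The change from *on* to *by* day 28 in 14.3 might be read as admitting children who respond early and then lose response. Sections 4.4, 9.1.1 and 14.1 require response on day 28, and 4.5 uses both words and then states the same rule. It is an editorial slip.

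Finally, the primary p-value is not the sole decision criterion: 14.2 bases the phase III decision on primary and secondary endpoints together.

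**Conclusion.** The point holds in two limited parts.

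- **Test.** Sections 14.2 and 14.3 prescribe different rejection rules, one patient apart (17 against 16 of 50), and give opposite verdicts at 16/50. This assumes a one-sample chi-squared test and that alpha 0.001 carries over to 14.3. False positives stay within the stated alpha under either rule.
- **Rates.** The 14% is exposure-only wherever it is explained, while the endpoint also requires response. At 75% to 96% response the composite historical rate would be 10.5% to 13.4%, so testing against 14% is conservative. The 42% is worded both ways. If it is exposure-only, power of the ≥17/50 rule is 0.50 at 79% response and 0.85 at 96%, instead of 0.90. If it is the composite rate, the stated power stands.

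The first part is certain from the text and small in effect. The second could matter more, but its size depends on a response rate that the documents do not give.

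**What to change.** 1. In 14.3, name the exact binomial test against 14% at two-sided alpha 0.001, with success at 17 or more of 50, and report an exact confidence interval.
2. In 4.1, 14.2 and 14.3, either state that 14% is an exposure-only rate used as a conservative null, or replace it with the proportion of low-risk children in the existing MAGIC cohort who met both the dose limit and day-28 response, and recompute the cut-off.
3. In the same sections, state whether 42% is the composite rate. If it is not, give the composite target and restate the power.
4. Change *by* to *on* day 28 in 14.3, to agree with 4.4.

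The cost is wording and, if the second option in step 2 is taken, one tabulation of existing data. It should be done before the primary analysis. The drawbacks are that a result of exactly 16/50 would not be significant against 14%, and that the restated power may be lower than 90%.
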